both using the modified intent-to-treat (mITT) study population and Last Observation Carried Forward (LOCF).

- An active treatment will be considered to be superior to the placebo if the difference in the means for the two treatment groups are statistically significant ($p < 0.05$) and the active treatment's mean percent reduction from screening/baseline is greater than that for placebo.
- Analysis of local irritation reactions (application site reactions).
- A descriptive analysis comparing the local irritation reactions (**application site reactions**) for each treatment group will be conducted to ensure that the test product is similar to the reference product with regard to the expected and unexpected application site reactions.
- Analysis of IGA scores:
 - Descriptive statistics using categorical methods to compare IGA Scores between each treatment group will be conducted and presented. No inferential analyses are planned.
- Summary of Subjects who terminate prematurely.
 - Reasons for premature termination will be summarized by treatment group.
- Concomitant medication.
 - The start and stop calendar date (e.g., mm/dd/yyyy) and study day (e.g., Day X) of concomitant medication used prior to and during the study will be provided in the data set in addition to the reason for the medication use. It should clearly be noted whether the medication was used prior to screening/baseline visit, during the study, or both.

Safety Analyses

Safety analyses will be conducted on the safety population. Safety Incidence of all adverse

events reported during the study will be summarized using the MedDRA dictionary by treatment group, body system, severity and relationship to study drug.

The report of AEs will include relatedness to treatment, date of onset, description of the AE, severity, action taken, outcome and date of resolution. Formal statistical evaluation(s) of the comparability of the two active treatment groups will be conducted with regard to the frequency and severity of any AE that occurs in at least 5% of the subjects in either active treatment group.

Application site reactions such as erythema, dryness, burning/stinging, erosion, edema, pain and itching will be summarized for the safety population by treatment group and study visit using frequencies and percentages of subjects.

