10.3.2 Safety Assessment

The extent of exposure will be summarized using descriptive statistics. No inferential analyses are planned.

Incidence of all adverse events reported during the study will be summarized using the MedDRA dictionary by treatment group, body system, severity, and relationship to study drug. The comparability of the Test and Reference treatment groups for the frequency and severity of any adverse event that occurs in at least 5% of the subjects in either treatment group will be evaluated using categorical methods.

The concomitant medications used will be summarized by treatment group.

Application site reactions such as erythema, dryness, burning/stinging, erosion, edema, pain and itching will be summarized for the safety population by treatment group and study visit using frequencies and percentages of subjects.

Safety analyses will be performed on the safety population. All safety data will be listed by treatment and Subject in data listings.

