7. STATISTICAL METHODS OF ANALYSIS

7.1 General Principles

All tables, figures, and listings will be produced in the landscape format.

In general, all data will be listed by treatment group, subject and visit where appropriate. The summary tables will also be stratified by, or have columns corresponding to, treatment group.

The total number of subjects in the treatment group (N) under the stated population will be displayed in the header of summary tables.

Data will be summarized using descriptive statistics for continuous variables. Unless otherwise specified, descriptive statistics will include number of subjects, mean, standard deviation, minimum, median, and maximum. The minimum and maximum statistics will be presented to the same number of decimal places as the original data. The mean and median will be presented to one more decimal place than the original data. The standard deviation will be presented to two more decimal places than the original data. The number of missing observations will be presented only if non-zero.

In summary tables of categorical variables counts and percentages will be used. The count [n] indicates the actual number of subjects in a particular category, which should always be less than or equal to the total number of subjects in the respective treatment group/population with known (non-missing) category [N]. Percentage will be obtained by: $\% = n/N*100$. Unless otherwise specified, all percentages will be expressed to one decimal place.

All statistical tests will be two-sided at a significance level of $\alpha = 0.05$, unless otherwise specified. No adjustment will be made for multiplicity.

Relative days will be calculated relative to the date of the first dose of study medication. Relative days will be calculated as follows only when the full assessment date is known (i.e., partial dates will have missing relative days).

For assessment on or after the day of the first dose of study drug:

Relative Day = Date of Assessment – Date of the First Dose of study Drug+1.

For assessment before the day of the first dose of study drug:

Relative Day = Date of Assessment – Date of the First Dose of study Drug.

All dates will be displayed in DDMMYYYY format.

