Summaries of AEs will be presented in alphabetical order of SOC and preferred terms. Additionally, TEAEs will be summarized by the preferred terms in the descending order of frequency in the total treatment group. In this table a p-value from Fisher's exact test comparing event rates between the Test and the Reference treatment groups will be provided for those preferred terms that have frequency > 1% in either Test or Reference group.

All information pertaining to adverse events noted during the study will be listed by subject, detailing verbatim, preferred term, system organ class, start date, stop date, severity, outcome, action taken, and causal relationship to the study drug. The adverse event onset will also be shown relative (in number of days) to the date of first administration of the study medication. In addition, the adverse event duration (if AE Stop Date is available) will be evaluated as below and presented (in number of days).

$$\text{AE Duration} = \text{AE Stop Date} - \text{AE Start Date} + 1$$

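### The SAP evaluates Test-versus-Reference adverse event comparability only by a Fisher p-value, with no difference estimate or confidence interval, so the planned output cannot support comparability

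*SAP*

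**What the plan says.** **Aim for adverse events.** Comparing safety across the three arms is an objective in Protocol section 2. The Protocol synopsis (Safety Analyses) states: "Formal statistical evaluation(s) of the comparability of the two active treatment groups will be conducted with regard to the frequency and severity" of any event reaching 5% in either active group. Protocol section 10.3.2 repeats this: "The comparability of the Test and Reference treatment groups for the frequency and severity of any adverse event" at or above that threshold is to be evaluated by categorical methods, which it does not name.

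**Method for adverse events.** In SAP section 7.7.1, "a p-value from Fisher's exact test comparing event rates between the Test and the Reference treatment groups will be provided", limited to "preferred terms that have frequency > 1% in either Test or Reference group". Frequency tables show counts and percentages by arm, including a table by maximum severity. The only comparison of Test with Reference is the Fisher p-value. SAP section 7.1 sets two-sided tests at 0.05 without multiplicity adjustment.

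**Application site reactions.** The synopsis calls this analysis descriptive, yet says it "will be conducted to ensure that the test product is similar to the reference product with regard to the expected and unexpected application site reactions". Protocol section 10.3.3.5 also specifies descriptive statistics. SAP section 7.7.4 gives counts, percentages and shift tables, with no contrast between arms.

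**Efficacy, for contrast.** Equivalence in lesion counts is judged by a 90% confidence interval lying within [0.80, 1.25] (SAP sections 5 and 7.6.2.1).

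**The concern.** The protocol's question is one of similarity, while the SAP's tool tests for a difference. A large Fisher p-value can mean that the arms are alike, or that there were too few events to tell. The p-value alone does not separate the two. The plan applies the right logic to efficacy, where an interval is set against limits, but has no counterpart for safety.

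At stake is how the safety objective is answered in the report. A reader would see arm percentages and a p-value, but nothing showing how large an excess of events under the generic the data still allow. Irritation matters here too. Protocol section 6.3 calls local reactions common, but records them as adverse events only if they worsen significantly, need medical intervention or lead to discontinuation. Most irritation would therefore not reach the Fisher table.

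**Working it through.** The plan states no power or precision for safety, so there is no figure of its own to reproduce.

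**Inputs**
- Two-sided Fisher's exact test at 0.05 (SAP sections 7.1 and 7.7.1).
- Screen: above 1% in either active arm (SAP section 7.7.1); at least 5% in the protocol.
- Arm sizes and allocation: redacted. *Assumption:* equal Test and Reference arms, n = 150 to 500 each.
- True event rates: not given. *Assumption:* Reference 1%, 2% or 5%, with Test at double that rate.

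**Method.** With a events in Test and b in Reference,

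power = Σ Bin(a; n, p_T) × Bin(b; n, p_R), summed over all pairs (a, b) with Fisher p < 0.05;

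miss rate = 1 − power.

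**Chance of missing a true doubling**

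| Reference vs Test | n = 150 | 200 | 300 | 400 | 500 |
|---|---|---|---|---|---|
| 1% vs 2% | 98% | 96% | 91% | 87% | 82% |
| 2% vs 4% | 91% | 87% | 77% | 68% | 60% |
| 5% vs 10% | 70% | 59% | 41% | 26% | 17% |

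Example: 5% vs 10% at n = 400 has power 0.737, so the miss rate is 1 − 0.737 = 26%.

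The first two rows concern terms that the SAP's 1% screen can admit. The third is the range to which the protocol's 5% commitment applies. There, a doubling is detected more often than not once each arm exceeds about 245.

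**What an interval would add, at an assumed 400 per arm** (Newcombe interval for the difference, log method for the risk ratio)
- 12 vs 4 events: 3.0% vs 1.0%, difference 2.0 points. Fisher is non-significant. The 95% interval runs from about 0 to 4.3 points; risk ratio 3.0 (0.98 to 9.22).
- 4 vs 4 events: difference 0, interval −1.7 to 1.7 points; risk ratio 0.25 to 3.97.
- 20 vs 20 events: difference 0, interval −3.1 to 3.1 points; risk ratio 0.55 to 1.83.

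The first two cases are both non-significant by Fisher. One leaves an excess of four points open and the other does not, which only the interval shows.

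**The case against.** **No decision rule is written.** A reader might infer that p above 0.05 will be reported as comparable. The documents do not say so. The SAP says only that the p-value is provided, there is no safety success criterion, and bioequivalence and superiority rest on lesion counts alone. This stands. The concern is that the output does not match the stated aim and that nothing guards against the misreading.

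**Low power is not general.** A reader might also infer that a doubled or tripled event rate would usually be missed. That is too broad. The arm sizes are redacted, 5% vs 10% is missed less than half the time from 300 per arm, and 5% vs 15% is missed about 20% of the time at 150 per arm and less often in larger arms. The severe miss rates belong to rare terms, which lie below the protocol's 5% commitment and enter only through the SAP's wider screen. This stands and limits the claim about size.

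**The information is recoverable.** Counts and denominators will be tabulated, so anyone can compute a difference and interval. That is true, and it makes this a reporting gap with no loss of data. A formal evaluation of comparability should still report its own estimate and precision.

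**Irritation was planned as descriptive.** It was, and severity distributions with shift tables are a legitimate descriptive method. Only the synopsis's stated purpose of ensuring similarity goes beyond what such tables can show. Intervals for every sign at every visit would be 7 × 3 = 21 post-baseline contrasts, which is more than the aim requires.

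**Conclusion.** The concern holds in a limited form. For adverse events, the SAP's only Test-versus-Reference statistic is a p-value from a test of no difference. It cannot support the comparability that the protocol sets out to evaluate, whatever the sample size.

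The practical size depends on redacted arm sizes and unstated event rates. For equal arms of 150 to 500, a doubling from 1% or 2% would be missed 60 to 98% of the time; for a doubling from 5% the miss rate falls from 70% to 17%. For commoner events in larger arms the Fisher test is reasonably sensitive, and the argument then rests on logic and precision more than on power.

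For application site reactions the gap is narrower: a descriptive analysis is given a purpose that it cannot meet without some measure of precision. The primary equivalence and superiority conclusions are not touched. This is a worthwhile, inexpensive improvement to the safety reporting.

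**What to change.** **SAP section 7.7.1.** For each preferred term already selected for comparison, add to the planned table the Test-minus-Reference difference in percentage of subjects with a two-sided 95% confidence interval, for example Miettinen-Nurminen. State that comparability is described from the estimate and its confidence limits, and that p of 0.05 or more is not evidence of similarity.

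If the Fisher p-value stays, say that the interval is the basis for interpretation, because the two can disagree at the margin. At 400 per arm, 59 vs 40 events is non-significant by Fisher, while the Newcombe interval for the difference (0.2 to 9.3 points) excludes zero.

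**SAP section 7.7.4.** Keep the analysis descriptive. Add one Test-minus-Reference difference with a 95% interval for each of the seven signs, using a single prespecified summary such as worst post-baseline severity. The sponsor should choose the severity cut before unblinding; the documents give none.

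**Cost.** A few columns in planned tables and a short SAP statement, with no new data or subjects. The downside is several unadjusted intervals, some of them wide, which should be labelled descriptive.

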8. CHANGES FROM PROTOCOL-SPECIFIED ANALYSES

The definition of the mITT population was expanded in the SAP.

Otherwise, there are no changes from the protocol-specified analyses.

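### SAP 7.7.1 has no Test-versus-Reference comparison of adverse event severity, which the protocol requires, and SAP section 8 does not declare this or the wider >1% testing threshold

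*SAP*

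**What the plan says.** **Protocol.** The Safety Analyses part of the synopsis states: "Formal statistical evaluation(s) of the comparability of the two active treatment groups will be conducted with regard to the frequency and severity of any AE", limited to an event "that occurs in at least 5% of the subjects in either active treatment group". Section 10.3.2 repeats the commitment for Test and Reference. It asks for categorical methods, names both attributes again, and covers "any adverse event that occurs in at least 5% of the subjects in either treatment group". Both places name frequency and severity, and both set the cut-off at 5%.

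**SAP.** Section 7.7.1 adds to the table of treatment-emergent events by preferred term "a p-value from Fisher's exact test comparing event rates between the Test and the Reference treatment groups", shown for terms with "frequency > 1% in either Test or Reference group". Severity appears in the same section as a count of events by severity and as a frequency table by maximum severity. Neither carries a between-group test.

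**Declared changes.** Section 8 of the SAP mentions the expanded mITT definition and then says: "Otherwise, there are no changes from the protocol-specified analyses".

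**The concern.** The two documents describe different analyses of the same safety question. The SAP covers the frequency half of the protocol's comparison with a p-value and gives no method for the severity half. It also applies a different threshold. Neither difference is declared.

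Comparing the safety of the three treatments is an objective in protocol section 2, while section 2 of the SAP lists only equivalence and superiority. Severity matters for a generic topical retinoid. The local irritation scores are summarised descriptively only (protocol 10.3.3.5, SAP 7.7.4), and protocol 6.3 records irritation as an adverse event only when it significantly worsens, needs intervention or leads to discontinuation. The adverse event severity comparison is therefore the one formal Test-versus-Reference comparison of severity that the protocol plans. If its method is not fixed before unblinding, it will either be left out or be chosen after the data are seen.

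**Working it through.** No figure in either document can be reproduced on this point, and the arm sizes are redacted. The main check is to set the texts side by side.

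| Element | Protocol (synopsis; 10.3.2) | SAP 7.7.1 | Declared in SAP 8? |
|---|---|---|---|
| Arms compared | Test v Reference | Test v Reference | no change |
| Frequency | compared | Fisher exact test | no change |
| Severity | compared | tabulated, no test | no |
| Threshold | at least 5% in either active arm | above 1% in either active arm | no |

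**Step 1: is a planned frequency test lost?** A term at 5% or more in an arm is also above 1% in that arm. The set of terms tested under the SAP contains the protocol's set at preferred-term level, so nothing is lost.

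**Step 2: is a planned severity comparison lost?** Yes. The protocol plans one for every term that reaches 5%, and the SAP text specifies none.

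**Step 3: how far does the lower threshold reach?** Assume n subjects per active arm. The smallest count that triggers a test is floor(0.01n) + 1 under the SAP and ceil(0.05n) under the protocol. The last column gives the two-sided Fisher p-value when the SAP's smallest count falls in one arm and the other arm has none.

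| n per arm (assumed) | Smallest count, >1% | Smallest count, ≥5% | p, smallest >1% count v 0 |
|---|---|---|---|
| 100 | 2 | 5 | 0.50 |
| 200 | 3 | 10 | 0.25 |
| 300 | 4 | 15 | 0.12 |
| 400 | 5 | 20 | 0.062 |
| 500 | 6 | 25 | 0.031 |
| 600 | 7 | 30 | 0.015 |

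**Step 4: are terms inside the 1% to 5% band uninformative?** Not in general. Two-sided Fisher p-values:

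- 6 v 0: about 0.03 at n = 200, 300 and 400, where 6 subjects are 3%, 2% and 1.5%.
- 9/300 v 0/300 (3% v 0%): 0.004.
- 12/300 v 3/300 (4% v 1%): 0.033.
- 16/400 v 4/400 (4% v 1%): 0.011.
- 8/200 v 2/200 (4% v 1%): 0.105.

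**Step 5: chance findings.** With m independent tests at 0.05, the nominal chance of at least one p < 0.05 is 1 − 0.95^m: 0.23 for m = 5, 0.40 for m = 10 and 0.64 for m = 20. Fisher's test is conservative, so the actual chance is lower. The number of added terms cannot be known from the documents.

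**The case against.** **Severity is still shown by arm.** This is true. SAP 7.7.1 plans a maximum-severity table by system organ class and preferred term, and SAP 7.1 puts treatment groups in columns. A reader might infer that severity goes unreported, and the documents do not support that. What is missing is the formal comparison.

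**Categorical methods may mean tables only.** Protocol 10.3.3.4 and 10.3.3.5 do use that phrase for descriptive work. But those sections say they are descriptive, and section 10.3.2 does not say so for adverse events. The synopsis settles the matter by calling the evaluation formal. The SAP itself reads the frequency half as calling for a p-value.

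**The 1% threshold might be read as an error in itself.** A reader might infer that it displaces a planned test, or that p-values for terms between 1% and 5% carry no information. Neither follows. Step 1 shows that no planned frequency test is removed. Step 4 shows that terms well inside the band can reveal a real imbalance. A term that only just triggers the test cannot reach 0.05 at the assumed 100 to 400 per arm, but it can at 500 or 600. Unadjusted testing is not a departure either, because protocol 10.1.3 and SAP 7.1 both rule out multiplicity adjustment. A return to 5% for the Fisher test would be a preference. What stands is that the extension is undeclared.

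**Few terms may reach 5%.** This is possible, given the restrictive rule in protocol 6.3 for recording irritation as an adverse event. It would make the analysis small but would not remove the commitment.

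**The table shells may contain a severity test.** They are a separate document and were not available. A method that the protocol requires should in any case be stated in the SAP.

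**Conclusion.** The point holds for severity and for section 8. The protocol plans a formal Test-versus-Reference comparison of adverse event severity for terms in at least 5% of either active arm, and SAP 7.7.1 specifies none. SAP section 8 is therefore wrong to say that nothing else changed. The wider Fisher threshold is a second undeclared change, but it only adds tests.

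The consequence is confined to safety: one protocol-planned analysis would not be done. The equivalence and superiority conclusions do not depend on it. The finding rests on unredacted text in both documents and needs no assumption about arm sizes. Those assumptions enter only the figures on the 1% threshold.

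**What to change.** In SAP 7.7.1, for preferred terms in at least 5% of subjects in either active arm, add a pre-specified categorical comparison of maximum severity between Test and Reference. Two workable choices, each with a limit that the SAP should state:

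- A Cochran-Mantel-Haenszel row-mean-scores test on none, mild, moderate and severe, the statistic that SAP 7.3 already uses for baseline IGA. It keeps all subjects, but including none mixes incidence with severity, so it partly repeats the Fisher test.
- The same test among subjects with the event. It isolates severity, but that subset is defined after randomisation, so it is not a randomised comparison.

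In SAP section 8, list the extension of the Fisher test to terms above 1% as a change from the protocol. The Fisher threshold itself can stay. If the sponsor would rather keep severity descriptive, that too must be listed in section 8 with a reason.

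The cost is a few sentences, one extra table column and a few more unadjusted exploratory p-values. No new data are needed, and the wording should be settled before unblinding.

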7.7.2 Vital Signs

Vital signs, including blood pressure, pulse rate, respiratory rate and body temperature will be documented at Visit 1, Visit 2, Visit 3 and Visit 4. Vital signs will be measured after the subject has rested in a seated position for about 5 minutes. Weight will be measured at Visits 1 and 4 as part of the physical examination.

Actual values and changes from baseline of each vital sign (including weight) will be summarized by visit and treatment group using descriptive statistics. All results will be listed.

7.7.3 Physical Examination

A brief physical examination will be performed at screening/baseline, Visit 4 End of Treatment/Early Discontinuation and during unscheduled visits where applicable. The physical examination will include, at a minimum, examination of the Subject's general appearance, skin, HEENT (head, eyes, ears, nose and throat), heart, lungs, musculoskeletal system, neurological system, lymph nodes, abdomen and extremities. Each body system will be classified as normal, abnormal not clinically significant or abnormal clinically significant.

Number and percentage of subjects with each assessment result will be summarized by body system, visit and treatment group. All results will be listed.

